**Aims, purpose, or objectives:**

We propose to conduct a pilot study on the safety and impact of two nature-based virtual reality (VR) interventions on levels of anxiety and inattention.

Paradigms like this have been used previously to study the impact of VR on anxiety but this specific intervention has not. Thus, it is reasonable to assume that it is feasible, but unique to the study of workplace anxiety and inattention, and in its design too.

The proposed investigation will apply two novel paradigms using proprietary VR (R-VR) interventions designed to reduce anxiety and inattention. We will explore whether this intervention is safe, and whether it can impact the stress, anxiety, and difficulty in focus of employees in the workplace. Results from this pilot study will be used to decide if a larger efficacy study with longer duration of daily VR experience will be developed.

**The primary aims:**

- 1) Evaluate the safety and acceptability of the R-VR
- 2) Evaluate the adherence to the R-VR
- 3) Evaluate the impact of using R-VR on anxiety and inattention levels
- 4) Compare the impact of two R-VR paradigms on anxiety and to correlate this impact with baseline self-efficacy

The major constructs that will be examined in this proposal are (1) Safety; (2) Anxiety; (3) Inattention; (4) Self-Efficacy. It is expected that this exploratory work will lay the foundation for future studies on anxiety and inattention interventions at work.

**Background:**

**Is anxiety in the workplace relevant?** According to large population-based surveys, up to 33.7 percent of the population is affected by an anxiety disorder during their lifetime. In the workplace, millennials and people who fall into the “Gen Z” category are especially vulnerable, and 54 percent of workers under 23 said they felt anxious or nervous due to stress in the preceding month.

While some anxiety may improve job performance by motivating people, many studies now document the detrimental impact of anxiety on job performance. Impostor syndrome, burnout, and decreased satisfaction with work are just some of the negative impacts of anxiety. Also, much research also demonstrates that the greater the anxiety, the lower degree of hope and sense of possibility, with a subsequent sense of demoralization. In fact, anxious CEOs may be risk-averse verging on paranoid.

Furthermore, anxiety disorders are also very costly. The total costs of anxiety disorders were approximately \$40 Billion in the US in the 1990s and € 74.4 billion for 30 European EU countries in 2010^14. The current costs are likely to be much higher.

**Do we really need an intervention for anxiety at work?** Although there are many conventional treatments for anxiety disorders, 40 percent of people who are treated relapse or are refractory. Also, the percentage of people

with anxiety disorders who seek help is lower than 50 percent. Having an ancillary and readily available intervention for state anxiety in the workplace is likely to be helpful.

**Why will we not focus on diagnoses per se?** The category of “anxiety disorders” has raised much controversy recently, and there is a trend to examine traits in research that correlate with biology rather than consider diagnostic categories. This is a feasibility study in a general population not focused on anxiety disorders but focused on the acceptability of such an intervention.

**Why will we use nature-based interventions?**

Studies indicate that forest walks are especially helpful in improving anxiety. Even short-term exposures to nature decrease anxiety and improve happiness and wellbeing.

In a recent systematic review, many studies indicate that VR was an effective form of therapy for mental disorders compared to “treatment as usual”. In addition, there are an increasing number of studies that have demonstrated that VR may be helpful for anxiety. Specifically, it has been shown to be useful where worry is excessive, for social anxiety, post-traumatic stress disorder, and panic attacks.

For these reasons, combining nature-based interventions with VR is a potentially feasible approach to decrease anxiety in the workplace.

While the exact mechanism is unknown, some preliminary data indicates that this might occur by shifting proportional power from higher Beta frequencies into lower Beta frequencies, and significantly reduced broadband Beta activity in the anterior cingulate cortex. And even after one session of VR, there is decreased activity in the dorsolateral prefrontal cortex and medial prefrontal cortex that increases over subsequent sessions.

### Study Design and Methods

**Design:** This is a single blinded randomized cross-over study. The participants will be randomly assigned the order of the paradigms viewed in the R-VR or as videos on the computer. The randomization will be through REDCap, as programmed by the study statisticians. The R-VR with the pre-programmed paradigms and corresponding non-VR videos will be labelled A through D. The coordinators will be informed via REDCap about which the experience to provide the participants for each of the study visits: A-D for Visits 1-4.

### Data Collection

- Participants will complete study surveys/questionnaires through REDCap. The coordinator will provide the iPad digital or paper copy version of the survey/questionnaire to the participant for the in-person visits and by email link or phone interview for the remote visits.
- Survey data collection in this study will utilize REDCap. The only anticipated paper source documents will be if participant chooses to complete surveys via paper copy or phone collection, which will then have select variables entered directly into the REDCap data entry system. All other data collection will be entered directly into this password protected system.

## Visit Flow and Timeline

Visit Number	Day 0	Day 1		Day 4		Day 7		Day 10	
	V0 	V1a 	V1b	V2a	V2b	V3a	V3b	V4a	V4b
		Consent + 0 day to +7 days from	Immediately following VR/Video	Prior to VR/Video	Immediately following VR/Video	Prior to VR/Video	Immediately following VR/Video	Prior to VR/Video	Immediately following VR/Video
Informed Consent	X 								
Inclusion/Exclusion	X								
Demographics Form	X								
Medical History	X								
Adverse Events	X	X		X		X		X	
Concomitant Medications	X	X		X		X		X	
R-VR Intervention			X		X		X		X
Brief Resilience		X		X		X		X	
Evaluate Response to the VR experience (HUMAN)		X	X	X	X	X	X	X	X
Emotional distress		X	X	X	X	X	X	X	X
Cognitive Function		X	X	X	X	X	X	X	X
Self-efficacy		X		X		X		X	
Anxiety		X	X	X	X	X	X	X	X
Satisfaction Survey									X

Consent can be completed digitally in person or through remote consenting

Visit 0 and Visit 1 can occur on same day or on separate occasions at the participant's convenience.

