## Assessments

### Study Entry Screen/Safety:

- Demographics Form: This form will collect demographics (age, sex, education, marital status, job title), and other lifestyle history of the research participant.
- Medical History Form: This form will collect history of comorbid conditions such as head injury, seizures, major mental illness or anything that could interfere with the VR experience (e.g. eye sight). This information will be collected via self-report and health record abstraction.
- Adverse Events: Pre-post measures will be obtained for dizziness; stomach awareness; headaches; eyestrain and lightheadedness; nausea; seizures in individuals with photosensitivity; disorientation; temporary (short term) loss of spatial awareness.
- Concomitant Medications: Current medications (name, dosing, and indications) will be collected at every patient encounter.

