- Self-efficacy (Short Form 4a – 4 items): This *PROMIS Self-efficacy Scale* defines self-efficacy as confidence in one's ability to successfully perform specific tasks or behaviors. It assesses confidence in one's ability to successfully perform specific tasks or behaviors related to one's health in a variety of situations. Each item on the measure is rated on a 5-point scale (1=I am not at all confident; 2=I am a little confident; 3=I am somewhat confident; 4=I am quite confident; 5=I am very confident)
- Satisfaction with the program: This questionnaire is adapted from *Was it Worth it Questionnaire (WIWI)* and the *Reulay Qualitative Survey (RQS)* to measure study and RV satisfaction. It will be administered to the participants prior to discharge after completing the intervention at the end of the study, probing their satisfaction with the research study. These data could be used to assess the feasibility of the intervention by asking the patient if the entire research experience was worth it for them.

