### Data Analysis

**Power Statement:** The sample size for this pilot investigation (N=24) was established after considering both the statistical implications and the amount of project effort and resources required to recruit and study this unique participant population.

**Data Analysis Plan:** Data related to participant recruitment will be summarized, including the frequency of calls and the reasons for failing screening criteria. In all cases, data will be summarized using mean  $\pm$  SD for continuous variables and frequency percentages for nominal variables. Details will be documented and summarized for any participants who experience adverse events or are unable to complete the 10-minute VR experience for any reason. The percentage of participants who undergo the initial VR experience (V2) but discontinue study participation without returning for the 2nd VR experience (V3) will be summarized and compared between scenes using Fisher's exact test. Anxiety, stress, cognition will be assessed immediately before/after and 24 hours following each VR experience. Within and between group comparisons will be performed using appropriate repeated measures analyses (e.g. paired t-test, repeated measures ANOVA) taking into account the two group repeated measures cross-over study design. In all cases, findings will be summarized using point estimates and corresponding 95% confidence intervals.

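### No adverse-event form is scheduled after the fourth session, so events that start or persist after it have no planned route into the safety data

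*Combined protocol and SAP*

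**What the plan says.** The header row of Visit Flow and Timeline reads "Visit Number Day 0 Day 1 Day 4 Day 7 Day 10". Each of the four session visits has an 'a' and a 'b' column. V2a, V3a and V4a are headed "Prior to VR/Video", and the 'b' columns are headed "Immediately following VR/Video". The adverse-event row, "Adverse Events X X X X X", has its five marks at V0, V1a, V2a, V3a and V4a. All the 'b' columns are blank in that row, and V4b is the last column.

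Three other places bear on timing:

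- Study Entry Screen/Safety: "Pre-post measures will be obtained for dizziness; stomach awareness; headaches; eyestrain and lightheadedness; nausea", followed by further symptoms. It gives no recall period and no delayed time point.
- Data Analysis: "Anxiety, stress, cognition will be assessed immediately before/after and 24 hours following each VR experience". Adverse events are not in that list, and the schedule has no 24-hour column.
- Data Collection says questionnaires can be completed "by email link or phone interview for the remote visits", but the schedule shows no remote visit after Day 10. On the satisfaction survey, which the schedule marks only at V4b, Outcomes says "It will be administered to the participants prior to discharge after completing the intervention at the end of the study". Participation therefore appears to end there.

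**The concern.** Safety is part of the first primary aim, and the pilot is meant to inform whether to build a larger study with more VR time per day. Data Analysis undertakes to document and summarise adverse events for any participant who has one.

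After sessions 1, 2 and 3 the participant returns and meets another adverse-event form. After session 4 there is no return. A headache or eyestrain that begins after the participant leaves on Day 10, or a symptom still present on leaving, has no scheduled point at which it would be recorded or its resolution noted. A summary over all sessions would count session 4 in the denominator without the same opportunity to observe events.

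This is separate from the conflict between the promised pre-post measurement and the blank 'b' columns. Adding an immediate form at V4b would settle that conflict but would still leave session 4 without a later check.

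**Working it through.** The plan gives no figure of its own here, so the check is a count from the schedule.

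**Inputs.** Session days 1, 4, 7 and 10, and the adverse-event marks (Visit Flow and Timeline). 24 participants randomised (Participant Information). Four experiences per participant, two VR and two video, in randomised order (Study Design and Methods).

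**1. Interval to the next form.** 4 − 1 = 3, 7 − 4 = 3 and 10 − 7 = 3 days. Later adverse-event forms after sessions 1, 2, 3 and 4: 1, 1, 1 and 0.

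**2. All sessions.** 24 × 4 = 96 sessions, of which 24 are session 4. 24/96 = 25% have no later form. This assumes full attendance but nothing about order.

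**3. VR sessions.** 24 × 2 = 48. The share at session 4 depends on the order:

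| Assumption about order | VR sessions at V4 | Share of 48 |
|---|---|---|
| Balanced (VR is last in 12 of the 24 possible orders) | 12 | 25% |
| Unrestricted randomisation, 95% range of Binomial(24, 0.5) | 7 to 17 | 14.6% to 35.4% |
| VR at V2 and V3, as Data Analysis states | 0 | 0% |
| Logical maximum | 24 | 50% |

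**4. Effect on what a clean result could show.** Under balance, each VR scene is last in 6 of 24 orders, so 24 − 6 = 18 sessions per scene have a later form. If no events are seen in n sessions, the one-sided 95% upper bound is 1 − 0.05^(1/n):

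- n = 18: 15.3%
- n = 24: 11.7%

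**5. Sensitivity to dropout (assumed rates; the plan gives none).** If a fraction d is lost after each session and r = 1 − d, the share of attended sessions without a later form is 1/(1 + r + r² + r³):

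- d = 5%: 1/3.710 = 27.0%
- d = 10%: 1/3.439 = 29.1%

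**The case against.** The strongest reply is that the contrast between sessions is partly inferred. No recall period is given, and the form at V2a, V3a or V4a may be no more than the pre half of the pre-post measure for that day's session. If it records only current symptoms, no session has three days of capture. This stands: a reader might infer a defined three-day follow-up for sessions 1 to 3, but the documents establish only that a form exists three days later. It does not remove the gap, because session 4 lacks even that form.

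Second, the 24-hour assessment implies some contact after a VR session at V4. That is a genuine contradiction with the schedule. As worded, however, the contact covers anxiety, stress and cognition, follows VR experiences only, and appears in no column.

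Third, a reader might state flatly that a quarter of VR sessions lack later safety data. The documents do not support that. Balance is not stated, and the V2 and V3 placement in Data Analysis would make the figure zero.

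Fourth, a reader might infer biased comparisons. A VR session at V4 is always a second VR exposure, so under balance 12 of 24 second exposures and 0 of 24 first exposures have no later form. But no first-versus-second comparison of adverse events is planned. With balanced order the gap falls equally on both VR scenes and both videos. With full attendance, every participant also has at least one VR session followed by a form.

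Finally, exposure is about 10 minutes, and the documents give no rate of delayed events. The number of events that would be missed is therefore unknown.

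**Conclusion.** The point holds as a gap in safety data collection. By the schedule as printed, session 4 has no adverse-event form after it, immediate or later, and no other section supplies one. The firm size is 24 of 96 sessions (25%), given full attendance. For VR it is 12 of 48 if order is balanced and 0 of 48 if VR is at V2 and V3; the plan must say which applies.

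The consequence is that events starting or persisting after session 4 can escape a primary safety aim. A bias between VR and video or between scenes is not shown, provided that order is balanced. Under unrestricted randomisation, chance imbalance at V4 could make the gap uneven. The change is worth making because it is cheap relative to what the pilot is meant to establish.

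**What to change.** - Add one remote adverse-event form, by REDCap email link or phone, about three days after V4 (10 + 3 = Day 13), matching the interval after the other sessions. Alternatively, if the 24-hour contact is kept, put it in the schedule and add adverse events to it after every session, video as well as VR, including session 4.
- Have the form ask about events since the last session, and count post-visit events over the same window for every session.
- Reconcile Visit Flow and Timeline, Study Entry Screen/Safety and Data Analysis on when adverse events are collected and at which visits VR can occur. State whether order is balanced across visits.
- If no contact is added, report post-visit adverse events for sessions 1 to 3 only, with those sessions as the denominator.

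The Day 13 option costs 24 short forms using tools already in the protocol. Participation lasts up to about three days longer and a few participants may not respond. Adding items to a 24-hour contact costs little if that contact already runs; if it must be set up for every session, it is up to 24 × 4 = 96 contacts. The last option is a change of wording only.

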## Assessments

### Study Entry Screen/Safety:

- Demographics Form: This form will collect demographics (age, sex, education, marital status, job title), and other lifestyle history of the research participant.
- Medical History Form: This form will collect history of comorbid conditions such as head injury, seizures, major mental illness or anything that could interfere with the VR experience (e.g. eye sight). This information will be collected via self-report and health record abstraction.
- Adverse Events: Pre-post measures will be obtained for dizziness; stomach awareness; headaches; eyestrain and lightheadedness; nausea; seizures in individuals with photosensitivity; disorientation; temporary (short term) loss of spatial awareness.
- Concomitant Medications: Current medications (name, dosing, and indications) will be collected at every patient encounter.

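### A rise in anxiety that does not stop a VR session, lead to dropout or get reported as an event enters no planned safety summary, and a favourable mean can hide it

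*Combined protocol and SAP*

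**What the plan says.** The first primary aim is to "Evaluate the safety and acceptability of the R-VR". The section Study Entry Screen/Safety sets out what is measured: "Adverse Events: Pre-post measures will be obtained for dizziness; stomach awareness; headaches; eyestrain and lightheadedness; nausea", followed by "seizures in individuals with photosensitivity; disorientation; temporary (short term) loss of spatial awareness". These are physical and orientation symptoms. No item covers anxiety, panic, distress or loss of focus.

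Anxiety (STAI), emotional distress and cognitive function are listed under Outcomes. Visit Flow and Timeline schedules all three before and immediately after each of the four sessions.

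For analysis, the Data Analysis section says of continuous variables "In all cases, data will be summarized using mean" and SD. It gives the paired t-test and repeated measures ANOVA as examples of the comparisons to be made, and says that "findings will be summarized using point estimates and corresponding 95% confidence intervals". At participant level it says "Details will be documented and summarized for any participants who experience adverse events or are unable to complete the 10-minute VR experience for any reason". It also reports the percentage who have the first VR experience but do not come back for the second, compared between scenes.

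Nowhere is a worsening of anxiety, distress or cognition defined or counted.

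**The concern.** The intervention is meant to change anxiety and inattention, so a participant who leaves a session more anxious has had an unwanted effect on the very thing being targeted. The plan measures this at every session but uses the scores only to judge average benefit. A scene that calms most people and unsettles a few could then be reported as effective, with the few visible in neither the efficacy result nor the safety result.

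According to the aims section, the pilot's results will decide whether to develop a larger efficacy study with longer daily VR exposure. That decision would be made without knowing how many participants responded badly.

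**Working it through.** The plan states no figure to reproduce: N = 24 is given without an effect size, SD or power. The check has four parts. All STAI changes below are assumptions, because the documents give none. STAI has 20 items scored 1 to 4, so a simple sum runs from 20 to 80.

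**1. Which participants reach a safety summary**

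| What happens after anxiety rises | Captured in Data Analysis? |
|---|---|
| The VR session cannot be completed | Yes, whatever the reason |
| The participant does not return for the second VR experience | Yes, in the discontinuation percentage |
| It is reported and recorded as an adverse event | Yes; the text does not limit adverse events to the listed symptoms |
| Session completed, participant returns, nothing reported, score rises | No |

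The first three routes need the participant to stop, leave or complain. The measured scores feed none of them.

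**2. Can the mean hide a minority?** Assume 20 participants change by -8 and 4 by +12.

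- Mean = (20 × -8 + 4 × 12) / 24 = -112 / 24 = -4.67.
- Sum of squares = 20 × 3.333² + 4 × 16.667² = 1333.3, so SD = √(1333.3 / 23) = 7.61.
- 95% CI = -4.67 ± 2.069 × 7.61 / √24 = -7.88 to -1.45; p = 0.006.
- Share worsened = 4/24 = 16.7% (exact 95% CI 4.7% to 37.4%).

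With random variation of SD 5 added around those values, the interval lies wholly below zero in about 78% of simulated trials with 4 worseners and in 99.8% with 2.

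A milder set of assumptions (-6 for improvers, +10 for worseners, each ±3) gives:

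| Worseners of 24 | Mean change | SD | 95% CI | p |
|---|---|---|---|---|
| 2 (8.3%) | -4.67 | 5.46 | -6.97 to -2.36 | 0.0004 |
| 3 (12.5%) | -4.00 | 6.54 | -6.76 to -1.24 | 0.006 |
| 4 (16.7%) | -3.33 | 6.82 | -6.21 to -0.45 | 0.025 |
| 5 (20.8%) | -2.67 | 7.59 | -5.87 to 0.54 | 0.099 |

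Up to 4 of 24 can rise by at least 7 points (10 - 3) while the mean still shows a significant fall. The SD moves only from 5.5 to 6.8 between 2 and 4 worseners, so it does not reveal them.

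**3. Why a count needs a threshold.** Suppose everyone responds alike, with normal changes of mean -4.67 and SD 7.61. The share showing any rise is Φ(-4.67 / 7.61) = Φ(-0.61) ≈ 27%, or about 24 × 0.27 = 6.5 participants. That exceeds the 4 true worseners in the first illustration. With no effect at all, about half would rise, ignoring ties. A count of any rise is therefore mostly noise.

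**4. What a count could show at N = 24.** Exact 95% intervals are 0% to 14.2% for 0/24, 1.0% to 27.0% for 2/24 and 4.7% to 37.4% for 4/24.

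**Related inconsistency.** The safety section promises adverse-event measures before and after. The schedule marks adverse events at V0 and in the pre-session columns (V1a to V4a) only. Nothing is marked immediately after a session, or at any time after the fourth. As the schedule stands, the repeated questionnaires are the only immediate post-session record that could show psychological worsening.

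**The case against.** A reader might infer that the safety list is purely physical, or that anyone whose anxiety rises is missing from every safety count. The documents support neither. Disorientation and loss of spatial awareness are not purely physical. The analysis text covers sessions that cannot be completed for any reason, counts non-returners after the first VR experience, and leaves the term adverse events open, so panic that is reported or that ends a session is covered. It also does not follow that a scene with some worseners would necessarily be reported as free of adverse events.

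The plan is not confined to group means either. Aim 4 correlates impact with baseline self-efficacy, responses are to be examined against the HUMAN form, and the satisfaction survey asks each participant about the experience. The statistical tests are named only as examples. But none of these defines or counts a worsening.

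The documents give no evidence that these scenes raise anxiety in anyone, and the illustration is an assumed two-group split. That is fair. The illustration shows only that the planned summaries could not tell such a split from a uniform benefit.

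Finally, this is a 24-person pilot, and individual changes could be tabulated at any time. That shows the change is cheap. But a threshold chosen after seeing the scores would carry less weight than one set beforehand.

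**Conclusion.** The point holds in a limited form. Worsened anxiety, distress or cognition is not among the adverse-event measures, and no planned analysis counts participants whose scores worsen. The gap is confined to those who complete the session, return and report nothing.

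Under the assumed changes above, up to 4 of 24 (17%) could worsen markedly behind a statistically significant mean improvement; with 5, under the milder assumptions, the mean result is no longer significant. The true frequency is unknown and may be zero.

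This is an inexpensive improvement to the reporting of a primary aim. The planned mean comparisons are not wrong in themselves.

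**What to change.** **Data Analysis, under aim 1.** Add a participant-level table for STAI, distress and cognition with:

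- the number and percentage whose score worsens from before to after each session by at least a threshold that the sponsor fixes, with its justification, before seeing the data;
- the same count for the same participants' video sessions, as the benchmark for ordinary fluctuation (each scene is shown in both formats, so the pairing can be made scene by scene);
- exact 95% intervals and the paired VR-minus-video difference;
- a listing or plot of individual changes.

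State the direction of worsening for each scale. The protocol gives it for distress but not for cognition. The distress form has been reworded and is described as unvalidated, so its threshold will need its own rationale.

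**Study Entry Screen/Safety.** State whether worsening beyond the threshold is reported as a safety finding.

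**Visit Flow and Timeline.** Reconcile the pre-post adverse-event measures with the schedule, which marks adverse events only at V0 and before sessions.

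**Cost.** The analysis change is one extra table, with no new participants, visits or questionnaires. Some rises will be chance, which the video count will show. The intervals will be wide at N = 24, and the safety summary may look slightly less favourable.

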## **Video Experience Procedure**

Participants will be scheduled for a 30-min office visit. After a verbal description of the study process and completion of IRB consent form, participants will complete the demographic and other baseline questionnaires.

The coordinator will instruct the participant on certain procedures dependent on the study participant's randomization and visit:

**R-VR Experience:** Study participant will be asked to complete a set of questionnaires, following completion they will be seated in a swivel chair in the center of the research room, given basic instruction on the VR headgear [*Oculus Quest*], and then offered the opportunity to experience the intervention event. The approximately 10 minute VR event involves one of two scenes (randomly selected by REDCap): Scene 1 is designed for relaxation in nature with natural scenery such as trees, streams and deer, or Scene 2 designed to help the participant focus with natural scenery such as glowing embers and fireflies. After a VR experience, the headgear will be removed and the participants will be asked to complete a second round of questionnaires.

**Computer Video Experience:** Study participant will be asked to complete a set of questionnaires, following by being seated at a computer and asked to watch a video with one of two scenes: (Scene 1) natural scenery such as trees, streams and deer; (Scene 2) natural scenery such as glowing embers and fireflies. After this viewing they will be asked to complete a set of surveys.

All will be remunerated up to \$40 at the end of their study participation. This amount will be prorated based on the number of visits completed

This process will provide a within-participant control, allowing us to investigate whether the VR experience is safe and results in significantly more change than the Video experience.

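### The visit schedule places every adverse-event check before exposure, so the promised pre-post measurement of VR symptoms has no post-exposure time point

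*Combined protocol and SAP*

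**What the plan says.** The Adverse Events entry under Study Entry Screen/Safety states: "Pre-post measures will be obtained for dizziness; stomach awareness; headaches; eyestrain and lightheadedness; nausea". The list goes on to seizures in photosensitive people, disorientation and short-lived loss of spatial awareness.

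The Visit Flow and Timeline table splits each of Visits 1 to 4 into an a column (before exposure) and a b column, headed "Immediately following VR/Video". The Adverse Events row is marked at V0, V1a, V2a, V3a and V4a. It is blank at V1b, V2b, V3b and V4b.

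Three other places bear on the point:

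- Video Experience Procedure says that after VR "the headgear will be removed and the participants will be asked to complete a second round of questionnaires". It does not say that symptoms are among them. The same section presents the within-participant control as "allowing us to investigate whether the VR experience is safe".
- The Data Analysis Plan says "Anxiety, stress, cognition will be assessed immediately before/after and 24 hours following each VR experience". Symptoms are not in that list.
- The Data Analysis Plan also says "Details will be documented and summarized for any participants who experience adverse events", and covers participants who cannot complete the VR session. It gives no collection time.

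The first primary aim is to "Evaluate the safety and acceptability of the R-VR". Results will be "used to decide if a larger efficacy study with longer duration of daily VR experience will be developed".

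**The concern.** A pre-post measure needs a reading on each side of the exposure. The schedule provides only the reading before it. The listed symptoms include effects that can pass quickly, and the protocol itself describes one of them as temporary. A query at the next visit, with no recall period stated, is a poor substitute for asking as the headset comes off.

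If coordinators follow the table, the intended comparison of symptoms after VR with symptoms after video cannot be made. Symptoms that clear within the session or before the next visit would be known only through recall or spontaneous report. The likely error is under-detection of VR side effects, in a pilot whose results feed a decision about longer daily VR exposure. A reading not taken in the session cannot be recovered later.

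**Working it through.** The plan gives no figure to reproduce. The check sets the table against the text and then counts.

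**Inputs**

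- Participants: 24 (Participant Information; Power Statement).
- Exposures per participant: 4, one at each of Visits 1 to 4. They are labelled A to D: two VR scenes and two matching videos (Design; Video Experience Procedure).
- Nominal days: 1, 4, 7 and 10 (Visit Flow and Timeline).
- Assumptions: full attendance, and each participant receives each of the four experiences once.

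**Reading the rows**

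| Row | Columns marked | b columns marked |
|---|---|---|
| Adverse Events | V0, V1a, V2a, V3a, V4a | 0 of 4 |
| Concomitant Medications | V0, V1a, V2a, V3a, V4a | 0 of 4 |
| Brief Resilience, Self-efficacy | V1a, V2a, V3a, V4a | 0 of 4 |
| HUMAN, Emotional distress, Cognitive Function, Anxiety | all a and b columns | 4 of 4 |
| R-VR Intervention | V1b, V2b, V3b, V4b | 4 of 4 |

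Four rows show how the table marks collection both before and after exposure. Adverse Events is not among them. Concomitant Medications, Brief Resilience and Self-efficacy are also blank after exposure, but no text promises a pre-post measure for those, so only Adverse Events contradicts its own description.

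**Counts as printed**

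- Exposures: 24 × 4 = 96, of which VR: 24 × 2 = 48.
- Same-session post-exposure symptom measure: 0 of 4 per participant, so 0 of 96 overall and 0 of 48 for VR.
- Exposures 1 to 3: 24 × 3 = 72, and 72/96 = 75%. The next scheduled query comes 4 − 1 = 7 − 4 = 10 − 7 = 3 days later.
- Exposure 4: 24 of 96 = 25%, with no later scheduled query.
- VR exposures at Visit 4: 0 or 1 per participant, so between 0 and 24 of the 48. The documents do not give the sequences, so this cannot be narrowed.

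**Does another section fill the gap?** The second round of questionnaires is described without naming symptoms, and the table that itemises that round leaves Adverse Events out. The before, after and 24-hour assessments in the Data Analysis Plan cover anxiety, stress and cognition only. Reading pre-post as visit to visit would still leave exposure 4 without a post measure.

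**The case against.** The strongest objection is about the table itself. Its day labels each cover an a/b pair and come out of the PDF as a label followed by a blank. A single X spanning both columns of a visit would come out the same way. Rows marked twice show only that those rows are unmerged. The extracted text cannot settle this for the Adverse Events row, and the point stands as a real uncertainty.

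Three further arguments have some weight:

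- The row has the same pattern as Concomitant Medications, which is collected once per encounter. The X may mean once per visit, with the assessment text supplying the timing. This is possible, but one mark per visit does not show a pre-post measure, and nothing tells coordinators to read it so.
- The table is loose. The intervention itself sits in columns headed as following the intervention, and the 24-hour assessments have no column. A blank cell is therefore weaker evidence than usual. The 24-hour sentence still does not mention symptoms.
- The assessment text states the requirement, and nothing says the table overrides it. The loss occurs only if staff follow the table.

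It is also fair to say that the counts are four blank cells multiplied by 24 participants. They measure missing readings, not missed symptoms. Some safety data would remain: queries at the next visit, spontaneous reports and failures to complete VR.

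None of this removes the conflict. No section says which of the two governs.

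**Conclusion.** The concern holds as the documents are printed. The assessment text promises symptom measures before and after exposure, and the schedule provides only those before. With N = 24 and full attendance, 0 of 96 exposures have a same-session post measure, 72 rely on a query nominally three days later, and 24 have no later scheduled query.

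This must be put right because it touches the first primary aim and the VR-versus-video safety comparison. The consequence is conditional on staff following the schedule as printed. The direction, toward under-detection, follows from the timing, but its size cannot be estimated from the documents. If the X was meant to span both columns, the defect is one of presentation and the correction is smaller.

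**What to change.** Reconcile the Visit Flow and Timeline table, the Adverse Events entry and the Data Analysis Plan.

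1. In the table, mark the symptom items listed under Adverse Events at V1b, V2b, V3b and V4b. Complete them with the post-exposure questionnaires already given there, using the same items as at V1a to V4a. If the existing X was meant to cover both columns, print it in both.
2. In the Data Analysis Plan, add one sentence: new or worsened symptoms, post against pre, will be summarised per exposure by condition (VR Scene 1, VR Scene 2, Video Scene 1, Video Scene 2).

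The cost is a few extra items for participants at four existing visits, one REDCap form repeated, a table correction and one sentence. No visits are added.
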